### 8.3.7.3. Study holding rules

The safety holding rules are defined in the Table 12. Holding rules 1a-d will be assessed by the investigator on a continuous basis. Meeting any of these holding rules will trigger a hold of study intervention administration irrespective of number of participants enrolled and/or timing of the event. Holding rules 2a-c will be assessed by the iSRC during the safety evaluations on unblinded data.

These holding rules have been written under the assumption that the safety data from all participants will be available. If the data from all participants are not available (i.e., in case a participant is lost to follow-up), then the holding rules will be assessed on a prorata basis (expressed as percentage of participants to be evaluated) i.e., 3 out of 6 sentinel participants or 30% of all participants, whichever is met earlier.

Of note, no formal holding rules will be applied for other safety data such as non-lifethreatening SAEs, missed visits due to study intervention related AEs, Grade 1 and Grade 2 solicited and unsolicited AEs in the 7-day follow-up period (Day 1 to Day 7) and unsolicited AEs collected from Day 8 to Day 31 after study intervention administration. However, if available, these data will also be reviewed by the iSRC to allow an overall assessment of the benefit/risk ratio of study intervention administration.

Holding rule	Event (per dose and per individual study group)	Number of participants to pause vaccination in all groups, pending further evaluation by iSRC
1a	Death or any life-threatening SAE regardless of causality	≥1
1b	Any non-life-threatening SAE that cannot be reasonably attributed to a cause other than vaccination as per investigator or sponsor assessment	≥1
1c	Any withdrawal from the study (by investigator or participant request) following a Grade 3 AE	≥1
1d	Any administration site or systemic solicited AE leading to hospitalization, OR Necrosis at the injection site, Each with an event onset within the 7-day (Day 1-7) post- vaccination period	≥1
2a*	Any Grade 3 solicited administration site events, with an event onset within the 7-day (Day 1-7) post-vaccination period	≥3/6 or 30%**
2b*	Any Grade 3 solicited systemic events, with an event onset within the 7-day (Day 1-7) post-vaccination period	≥3/6 or 30%**
2c*	Any Grade 3 unsolicited AE, that can be reasonably attributed to the vaccination as per investigator or sponsor assessment, with an event onset within the 7-day (Day 1-7) post-vaccination period OR Any Grade 3 or above abnormality in pre-specified hematological or biochemical laboratory parameters with an event onset within the 8- day (Day 1-8) post-vaccination period except for non-clinically significant leukopenia	≥2/6 or 10%***

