# 1. PROTOCOL SUMMARY

# 1.1. Synopsis

**Rationale:** GSK is developing a novel mRNA vaccine platform where the SARS-CoV-2 Omicron variant S glycoprotein will be used as an antigen model (hereafter referred to as mRNA-CR vaccines). This mRNA vaccine platform development includes several mRNA constructs (mRNA-CR-XX) currently under development that will be progressing into clinical research in humans.

**Objectives, endpoints and estimands:** This exploratory, FTIH study is to evaluate the safety, reactogenicity and immune responses of the mRNA-CR-04 vaccine construct when administered in healthy adults previously vaccinated with SARS-CoV-2 mRNA vaccines. For details on objectives, endpoints and estimands, refer to Section 3.

**Overall design:** This will be a Phase 1, observer-blind, randomized, placebo-controlled, multicenter, dose-escalation study evaluating in Part A of the study, 3 doses ( $10 \mu g$ ,  $30 \mu g$ , and  $100 \mu g$ ) of the mRNA-CR-04 (Omicron BA.5 strain) vaccine. Approximately 72 participants will be enrolled with 24 participants per group (Group 1, Group 2 and Group 3). Within each group, participants will be randomly assigned in a 3:1 ratio to receive:

- investigational mRNA-CR-04 vaccine (SPK001-AC01 mRNA-LNP) or
- saline placebo.

For each group, 8 sentinel participants will first be enrolled and vaccinated. Enrollment of participants in Group 1 and Group 2 will be done in parallel with the first participant to be enrolled in Group 1. Only if no safety signal is observed, vaccination of the non-sentinel participants in that group will continue. If no safety signals observed in sentinel participant in Group 1 and Group 2, enrollment, and vaccination of the sentinel participants in Group 3 will be initiated. Refer to Section 4.1 and Figure 1 for more details on the study design.

Part B of the study will commence only after all Part A participants have completed their Day 15 study visits and the Day 15 interim analysis is completed. In Part B, 2 doses (3  $\mu$ g and 10  $\mu$ g) of the mRNA-CR-04 (Omicron BA.5 strain) vaccine will be evaluated. Approximately 42 participants will be enrolled in parallel in Part B and there will be no sentinel participants. Part B participants will be randomly assigned in a 3:3:1 ratio to receive:

- 3 µg investigational mRNA-CR-04 vaccine (SPK001-AC01 mRNA-LNP) or
- 10 µg investigational mRNA-CR-04 vaccine (SPK001-AC01 mRNA-LNP) or
- saline placebo.

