# 4. STUDY DESIGN

# 4.1. Overall design

**Experimental Design:** Phase 1, observer-blind, randomized, placebo-controlled, multicenter, dose-escalation study to evaluate in Part A of the study, 3 doses (10  $\mu$ g, 30  $\mu$ g, and 100  $\mu$ g) of the mRNA-CR-04 (Omicron BA.5 strain) vaccine (Figure 1) in 3 groups (Group 1, Group 2 and Group 3) (Table 4). Part B of the study will commence only after all Part A participants have completed their Day 15 study visits and the Day 15 interim analysis is completed. In Part B (Table 5), 2 doses (3  $\mu$ g and 10  $\mu$ g) of the mRNA-CR-04 (Omicron BA.5 strain) vaccine will be evaluated (Figure 1). The study will be conducted in the United States (US).

Duration of the study: Approximately 6 months after dosing.

**Sentinel dosing**: In Part A of the study, each group will have 8 sentinel participants (6 receiving the mRNA-CR-04 vaccine and 2 receiving a placebo) who will be enrolled and

vaccinated in each group. The first and second sentinel participant in each group will be vaccinated and followed-up for 24 hours before the next sentinel participant can be vaccinated. Vaccination of the remaining sentinel participants in the same group will then continue with an interval of at least 60 minutes between participants. Additionally, an interval of at least 60 minutes will be maintained between the vaccination of sentinel participants across groups.

**Dose-escalation:** In Part A of the study, enrollment of participants in Group 1 and Group 2 will be done in parallel with the first participant to be enrolled in Group 1. All safety data up to Day 8 post-vaccination from sentinel participants in both groups will be reviewed by the iSRC (unblinded review). The iSRC members will determine whether any of the pre-defined holding rules are met or if there is any other safety signal. If no safety signal is observed, vaccination of the non-sentinel participants in that group will continue. If no safety signal observed from sentinel participants in Group 1 and Group 2, enrollment and vaccination of the sentinel participants in Group 3 will be initiated. In Part B, irrespective of dose, all participants in the three study groups will be enrolled in parallel.

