## 8.3.7.1. Staggered administration of study intervention

Part A of the study will be conducted in a staggered manner to ensure maximum safety of the participating participants.

- Within each group, 8 sentinel participants (6 receiving the mRNA-CR-04 vaccine and 2 receiving the placebo) will first be enrolled and vaccinated.
- Enrollment of participants in Group 1 and Group 2 will be done in parallel with the first participant to be enrolled in Group 1. The first and second sentinel participant in each group will be vaccinated and followed-up for 24 hours before the next sentinel participant can be vaccinated. If no safety concerns are identified (as confirmed through individual phone call TC1, see Table 1), vaccination of the remaining sentinel participants in the same group will then continue with an interval of at least 60 minutes between participants. Additionally, an interval of at least 60 minutes will be maintained between the vaccination of sentinel participants across groups.
- If no safety concerns are identified by the iSRC during the review of unblinded Day 8 safety data of sentinel participants from Group 1 and Group 2, the remaining participants in these groups may receive the study intervention without limitation of the number of participants per day or the time between consecutive participants. Additionally, vaccination of sentinel participants in Group 3 may be initiated.
- If no safety concerns are identified by the iSRC review of unblinded Day 8 safety data of sentinel participants from Group 3, the remaining participants in Group 3 may receive the study intervention without limitation of the number of participants per day or the time between consecutive participants.

All participants will be closely observed (visibly followed, no specific procedure) during the 60 minutes after dose administration.

In addition to iSRC, blinded data will be reviewed by the SRT. The SRT and iSRC will meet regularly to review safety data throughout the study and may request escalation to the GSB to address any potential safety concerns or study holds at any point during the study. See Section 8.3.7.3.

In Part B of the study, irrespective of dose, all participants will be enrolled in parallel, and the SRT will also be able to review unblinded data.

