#### Table 12Study holding rules

AE: Adverse event; iSRC: Internal safety review committee; SAE: Serious adverse event.

\*Refer to the FDA guidance for industry "Toxicity grading scale for healthy adults and adolescent volunteers enrolled in preventive vaccine clinical trials" [FDA, 2007]. Any laboratory parameters not listed in Section 10.2.2 will not be graded and will be assessed on case-by-case basis.

\*\*3/6 sentinel participants or 30% of all participants, whichever is met earlier.

\*\*\*2/6 sentinel participants or 10% of all participants, whichever is met earlier.

Rule 2a-2c will be analyzed and reviewed during the scheduled iSRC meetings. During these scheduled iSRC meetings, iSRC will decide to:

- allow for dosing of the remaining non-sentinel participants (12 receiving mRNA-CR-04 and 4 receiving placebo) within the same group
- allow for randomization of the sentinel participants in the next group.

More details on the composition, objectives, and responsibilities of the iSRC, and the schedule and conduct of the iSRC meetings will be described in the iSRC charter.

If a holding rule is met, the investigator must suspend enrollment and administration of the study intervention and inform the CRO team immediately (holding rules 1a-d). Refer to Table 16 for contact information.

The CRO team will inform the investigator if holding rules 2a-c are met. Investigators will be responsible to inform the IRB/IEC if a holding rule has been met.

The following communication sequence must be followed when a holding rule 1a-1d is met:

- The concerned site staff must put study intervention randomization and administration on hold.
- The concerned site staff must immediately inform the CRO team contact defined in the Section 8.4.6.
- Enrollment and intervention allocation through IRT will be stopped on a study level.
- The CRO team will inform all investigators about the stopping of enrollment and intervention.
- All informed site staff will confirm to the CRO team that action has been taken providing appropriate documentation to the CRO team.
- The CRO team will inform GSK and provide the blinded data to GSK's CSL for further SRT and GSK GSB review.
- The CRO team will forward the relevant unblinded safety information to iSRC for evaluation.

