#### **Risk assessment:**

- Figure 2 illustrates that with 6 participants receiving the mRNA-CR-04 vaccine per group:
  - Rule 1: when at least 1 SAE is observed within 6 participants receiving the mRNA-CR-04 vaccine, there is 90% probability of not holding for a 1.7% SAE true incidence and 80% (=1-20%) probability of holding it for an SAE true incidence >23%.
  - Rule 2a-2b: when at least 3 participants with an AE are observed within 6 participants receiving the mRNA-CR-04 vaccine, there is 90% probability of not holding for a 20% AE true incidence and 80% (=1-20%) probability of holding it with a true AE incidence >58%.
  - Rule 2c: when at least 2 participants with an AE are observed within 6 participants receiving the mRNA-CR-04 vaccine, there is 90% probability of not holding for a 9% AE true incidence and 80% (=1-20%) probability of holding it with a true AE incidence >42%.
  - With 18 participants receiving the mRNA-CR-04 vaccine, and rule 1 (1/18), there is 90% probability of not holding for a 0.59% AE true incidence and 80% (=1-20%) probability of holding it with a true incidence >8.5%.

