# Figure 2 Probability of not meeting holding rules 1 and 2 for 8 participants per study group

## 8.3.7.4. SRT and iSRC evaluation

The study will be overseen by an iSRC operating under a charter. Core members of the iSRC will include a GSK safety physician, a CSL and a biostatistician who are not otherwise involved in the conduct of the project. The iSRC safety reviews will be conducted using unblinded data. The iSRC will have access to the participant randomization and will review unblinded data.

In addition to the iSRC, the project SRT will review blinded data until the Part A Day 15 interim analysis, and unblinded data subsequently, on a regular basis throughout the study.

The iSRC will review accumulated unblinded safety data of the sentinel participants of each group up to 7 days post-vaccination. The iSRC will include all safety data sources in their Day 8 safety review (i.e., solicited safety data, unsolicited safety data, SAEs and AESIs, as well as laboratory safety data). If no pre-defined holding rule is met (refer to Section 8.3.7.3) or if no safety signal is observed the remaining participants in the group can be vaccinated and vaccination in the next group can be initiated.

In case the iSRC, through the in-stream data monitoring of all the accumulated safety data available detects that a holding rule is met, the study vaccination will be temporarily paused in all study groups and sites pending review of safety data by the iSRC. The iSRC will make relevant recommendations to the GSB chair(s), who will make the final decision whether vaccination can be safely resumed or not.

In addition, at any time during the study, if one of the holding rules 1a through 1d (refer to Table 12 for details) is met, the investigator will immediately inform the CRO team. Vaccination will be paused and an urgent ad-hoc meeting of the iSRC will be called to thoroughly review the event(s) and recommend to the GSB whether vaccination can be safely resumed or not. The GSB chair(s) will make the final decision whether vaccination can be safely resumed or not.

In Part B of the study, the iSRC will only be requested to review unblinded data if a study holding rule is met or if the SRT identifies a safety concern through in-stream data monitoring of unblinded data.

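### The missing-data sentence for the holding rules prints only the 3/6 or 30% limit of rules 2a-2b, in conflict with the 2/6 or 10% that Table 12 sets for rule 2c

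*Protocol*

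**What the plan says.** Protocol section 8.3.7.3 opens with "The safety holding rules are defined in the Table 12". It assumes complete safety data, then gives one instruction for incomplete data: the holding rules are assessed pro rata, as a percentage of the participants to be evaluated, "i.e., 3 out of 6 sentinel participants or 30% of all participants, whichever is met earlier". The sentence names no rule and gives no other limit.

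Table 12 counts participants, per dose and per study group, and has three kinds of limit:

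- Rules 1a-1d: 1 or more participants.
- Rules 2a-2b (Grade 3 solicited events): 3 of 6 sentinels or 30%.
- Rule 2c: "2/6 sentinel participants or 10% of all participants, whichever is met earlier".

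The Risk assessment text in the same section also evaluates rule 2c on the smaller count, "when at least 2 participants with an AE are observed within 6 participants receiving the mRNA-CR-04 vaccine".

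For Part B, the Synopsis (1.1) states: "Approximately 42 participants will be enrolled in parallel in Part B and there will be no sentinel participants". Only the percentage limits can operate there. The SAP has no holding-rule text that settles the matter.

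**The concern.** The figures in the missing-data sentence equal the Table 12 limit for 2a-2b and contradict the one for 2c. Table 12 makes 2c stricter than the reactogenicity rules, and the sentence as printed removes that difference in exactly the case it governs. A specific instruction for incomplete data can reasonably be taken to override the general table, so one reader may apply 10% to rule 2c and another 30%.

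At stake is a numeric safety trigger in a first-in-human study: meeting it pauses vaccination in all groups. The percentage carries most weight in Part B, which has no sentinel stage and where, under section 8.3.7.4, "the iSRC will only be requested to review unblinded data if a study holding rule is met" or if the SRT identifies a safety concern in its own monitoring of unblinded data.

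**Working it through.** **Inputs.** Limits from Table 12 and the missing-data sentence; 18 vaccinees per dose group (Schema, 1.2); 6 vaccinated sentinels per Part A group (4.1). Assumptions: percentages are taken over evaluable vaccinees in one dose group, and participants are independent with a common incidence p. The evaluable numbers 12, 16 and 17 are scenarios, not figures from the documents.

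**Formulas.** Trigger r = the smallest whole number not below f × n, where f is the limit and n the evaluable number. Chance of meeting the trigger = 1 − Σ C(n,j) p^j (1−p)^(n−j), summed over j = 0 to r−1.

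**1. The plan's own figures for 2c (2 of 6).** At p = 9%, the chance of not holding is 0.91^6 + 6 × 0.09 × 0.91^5 = 0.568 + 0.337 = 90.5% (plan: 90%). At p = 42%, the chance of holding is 79.7% (plan: 80% above 42%). Both agree.

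**2. Rule 2c by percentage, as in Part B.**

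| Evaluable | Trigger at 10% | Trigger at 30% | Chance at p = 20% (10% vs 30% limit) | Chance at p = 30% (10% vs 30% limit) |
|---|---|---|---|---|
| 12 | 1.2 → 2 | 3.6 → 4 | 72.5% vs 20.5% | not computed |
| 16 | 1.6 → 2 | 4.8 → 5 | 85.9% vs 20.2% | 97.4% vs 55.0% |
| 17 | 1.7 → 2 | 5.1 → 6 | 88.2% vs 10.6% | 98.1% vs 40.3% |

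Worked row, n = 12, p = 20%: the terms for j = 0 to 3 are 0.0687, 0.2062, 0.2835 and 0.2362. At least 2: 1 − 0.2749 = 72.5%. At least 4: 1 − 0.7946 = 20.5%.

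Twelve evaluable could be 13 dosed with one lost, leaving 18 − 13 = 5 still to be dosed. Seventeen evaluable with one lost means that all 18 are dosed. The gap comes from the percentage and not from the lost participant: 10% and 30% of 18 also give 2 and 6.

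**3. Full Part A group, 17 evaluable, 30% reading.** The sentinel branch also counts. With 6 sentinels and 11 others, the trigger is 3 of 6 or 6 of 17: 16.1% at p = 20% and 46.8% at p = 30%. If the missing vaccinee is a sentinel (3 of 5 or 6 of 17): 13.6% and 43.9%. The Table 12 limit reduces to 2 of 17 in both cases: 88.2% and 98.1%.

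**4. Sentinel review at p = 42%.** With 5 evaluable sentinels, 50% needs 3 and 33.3% needs 2: 35.3% versus 69.7%. If instead 30% of those evaluated controls, 2 of 5 still triggers and nothing is lost. With 4 evaluable, both sentinel fractions need 2 (55.9%), so there is no difference.

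**The case against.** The strongest reply is that Table 12 already answers the question. Section 8.3.7.3 names it as the definition; pro-rating a rule keeps that rule's own proportion and cannot turn 10% into 30%; and the printed figures cannot apply to rules 1a-1d, which hold at one participant. On this view the sentence illustrates 2a-2b and the fault is one of drafting. As an account of intent this stands. It does not remove the conflict, because the sentence presents its figures as the meaning of pro-rating for the rules in general and no other text gives the 2c version. The iSRC charter may do so, but it is not among the documents.

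Two further points stand and limit the consequence. First, each participant receives one dose and Part B enrols in parallel, so at 16 or 17 evaluable there is little dosing left to pause. The part-way case at 12 is the more relevant one. Second, the numeric rule is not the only safeguard. In the Part A dose-escalation review, "The iSRC members will determine whether any of the pre-defined holding rules are met or if there is any other safety signal" (4.1). In Part B, "the SRT will also be able to review unblinded data" (8.3.7.1), and a concern it raises goes to the iSRC. Section 8.4.4.2.1 adds an ad hoc iSRC for any probable or definitive myocarditis or pericarditis case.

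A reader might infer that the protocol loosens 2c to 30% whenever a participant is lost, or that dosing would continue with the complements of the chances above. The documents support neither: the 10% limit is explicit in Table 12, and the calculations give only the chance of meeting one numeric trigger.

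**Conclusion.** The inconsistency is real and should be corrected. It is a conflict of wording on an operative safety threshold, probably unintended. If the sentence is followed literally for 2c, the trigger in a dose group rises from 2 to 4 participants with an event at 12 evaluable vaccinees, and from 2 to 6 at 17. At 20% incidence, the chance of meeting it falls from 72.5% to 20.5% and from 88.2% to 10.6% respectively. At sentinel review the effect depends on which branch controls and can be nil.

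These sizes rest on the literal reading, on evaluable vaccinees in one dose group as the denominator (the text does not say whether placebo recipients count), and on assumed numbers evaluable. The practical effect is limited by the late stage of dosing at the larger numbers and by the other routes to review. The documents do not show that a 2c signal would go unnoticed.

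**What to change.** Replace the figures in the missing-data sentence with text to this effect:

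*Each of rules 2a-2c is assessed pro rata against its own Table 12 limit. At sentinel review: 50% (2a-2b) or 33.3% (2c) of evaluable vaccinated sentinels. Beyond sentinel review, and in Part B: 30% (2a-2b) or 10% (2c) of evaluable vaccinees in the dose group. Rules 1a-1d are unchanged at 1 or more participants. The 10% and 30% limits are not applied to the sentinel subset alone.*

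The last sentence is needed. If 10% of all evaluable participants could be met at sentinel review, 1 of 6 (16.7%) would trigger a hold. At 9% incidence the chance of a hold would then be 1 − 0.91^6 = 43.2%, against the 9.5% implied by 2 of 6, and the plan's stated 90% chance of not holding would be lost.

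Early in Part B, 10% of 10 or fewer evaluable vaccinees is met by one participant. That follows from Table 12 as it stands, and the sponsor should confirm that it is intended.

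The cost is a short wording change in the protocol, mirrored in the iSRC charter if needed. It requires no extra participants or procedures.

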#### Table 12Study holding rules

AE: Adverse event; iSRC: Internal safety review committee; SAE: Serious adverse event.

\*Refer to the FDA guidance for industry "Toxicity grading scale for healthy adults and adolescent volunteers enrolled in preventive vaccine clinical trials" [FDA, 2007]. Any laboratory parameters not listed in Section 10.2.2 will not be graded and will be assessed on case-by-case basis.

\*\*3/6 sentinel participants or 30% of all participants, whichever is met earlier.

\*\*\*2/6 sentinel participants or 10% of all participants, whichever is met earlier.

Rule 2a-2c will be analyzed and reviewed during the scheduled iSRC meetings. During these scheduled iSRC meetings, iSRC will decide to:

- allow for dosing of the remaining non-sentinel participants (12 receiving mRNA-CR-04 and 4 receiving placebo) within the same group
- allow for randomization of the sentinel participants in the next group.

More details on the composition, objectives, and responsibilities of the iSRC, and the schedule and conduct of the iSRC meetings will be described in the iSRC charter.

If a holding rule is met, the investigator must suspend enrollment and administration of the study intervention and inform the CRO team immediately (holding rules 1a-d). Refer to Table 16 for contact information.

The CRO team will inform the investigator if holding rules 2a-c are met. Investigators will be responsible to inform the IRB/IEC if a holding rule has been met.

The following communication sequence must be followed when a holding rule 1a-1d is met:

- The concerned site staff must put study intervention randomization and administration on hold.
- The concerned site staff must immediately inform the CRO team contact defined in the Section 8.4.6.
- Enrollment and intervention allocation through IRT will be stopped on a study level.
- The CRO team will inform all investigators about the stopping of enrollment and intervention.
- All informed site staff will confirm to the CRO team that action has been taken providing appropriate documentation to the CRO team.
- The CRO team will inform GSK and provide the blinded data to GSK's CSL for further SRT and GSK GSB review.
- The CRO team will forward the relevant unblinded safety information to iSRC for evaluation.
- Based on the recommendation from iSRC, GSK's GSB will make the decision whether the study can resume, be modified, or stopped. GSK will notify the CRO team on this decision. The CRO team will notify all investigators on this decision.
- Depending on the outcome of the safety evaluation, the study will be re-started, terminated, or resumed under a protocol amendment.

The following communication sequence must be followed when a holding rule 2a-2c is being met:

- The study CSL will ensure that the CRO team is notified upon meeting holding rules 2a-2c.
- The CRO team will inform all the sites that a holding rule is met. Following this notification, the study intervention administration should be put on hold.
- All informed site staff will confirm to the CRO team that action has been taken providing appropriate documentation to the CRO team.
- GSK will further evaluate the case with the iSRC and GSK GSB and will take the decision to stop or to restart the study intervention administration or to amend the protocol. GSK will notify the CRO team on this decision and the CRO team will inform all site staff.

